#### 8.6.2.3 Urinalysis

pH, glucose, ketones, blood, protein, leukocytes, nitrites, bilirubin, urobilinogen, and specific gravity.

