## 9.4.3.4 Clinical Laboratory

Laboratory data (absolute values and change from baseline) will be summarized. In addition, the number and percent of subjects below, within, and above the laboratory reference ranges will be summarized by visit. Shift tables will be generated using the reference ranges.

Abnormal laboratory values from tests performed on the baseline visit will not be considered as TEAEs, because the sample collection will be conducted before study drug administration.

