10.3. Laboratory Evaluations

The hematology, chemistry laboratory analyses, and urinalyses will be performed at a central laboratory. Reference ranges will be supplied and used by the investigator to assess the laboratory data for clinical significance and pathological changes.

Laboratory assessments are performed at Screening, Baseline, Week 4, Week 8, Week 12, Week 16, Week 24 follow-up, Unscheduled Visits and Early Termination Visit.

The following parameters are reported for laboratory data.

- **Hematology:** Hemoglobin, hematocrit, white blood cell (WBC) count (with differential including eosinophils), red blood cell (RBC) count, platelet count, and mean cell volume (MCV).
- Chemistry: Creatinine, aspartate aminotransferase (AST), alanine aminotransferase (ALT), gamma glutamyltransferase (GGT), alkaline phosphatase, lactate dehydrogenase (LDH), total bilirubin, direct bilirubin, creatinine phosphokinase ([CPK], CPK isoenzyme test will be performed only if CPK is elevated to > 2.5 × ULN), albumin, total protein, uric acid, sodium, potassium, calcium, chloride, glucose, urea, total cholesterol, triglycerides, low-density lipoprotein (LDL), and high-density lipoprotein (HDL).

- **Urinalysis:** pH, glucose, ketones, blood, protein, leukocytes, nitrites, bilirubin, urobilinogen, and specific gravity.
- For hematology and chemistry, descriptive statistics by visit and changes from baseline for each
 parameter using the results in standardized international (SI) units will be presented in summary
 tables. Urinalysis parameters will be summarized categorically by visit with percentage based on the
 number of subjects with available data at the visit. By visit summaries will be performed at all visits
 (scheduled visits only) from baseline. Last post-baseline results, minimum and maximum postbaseline values during treatment period will also be included in by visit summary tables.
- Shift tables will be provided for hematology and chemistry by visit (scheduled visits only) and last post-baseline results during treatment period will also be included in the shift tables. Hematology and chemistry results will be classified as low (L), normal (N), and high (H) by the laboratory parameter's normal range. Shift from baseline using low, normal, high will be provided by visit for hematology and chemistry parameters and will also presented for minimum and maximum post-baseline values.

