- In addition, summary of hematology, chemistry and urinalysis using potentially clinical significant ranges will be provided by visit. Potentially clinically significant laboratory ranges are presented in section 21 (Potentially clinically significant ranges for laboratory tests).

Distribution of Aspartate Aminotransferase (AST), Alanine Aminotransferase (ALT), Alkaline Phosphatase (ALP), Total bilirubin and Creatinine Phospokinease (CPK) will be displayed graphically with maximum post-baseline values. Also spaghetti plots over time will be displayed graphically for those five parameters.

By-subject listing for subjects with at least one abnormal results (out of reference range) will be provided for hematology and clinical chemistry.

By-subject listing for subjects with at least one potentially clinically significant results will be provided for hematology, clinical chemistry and urinalysis.

All laboratory data will be listed.

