14.3.3		Narratives of Deaths, Other Serious and Certain Other Significant Adverse Events	·		
14.3.4		Laboratory Value			

Header	Table Number	Name	Analysis Population	Interim Analysis	IDMC
14.3.4.1		Clinical Laboratory Data		1	
14.3.4.1.1		Hematology Data			
	14.3.4.1.1.1	Summary of Laboratory Data - Hematology	Safety Population	Yes	Yes
	14.3.4.1.1.2	Shift from Baseline for Hematology by Reference Range	Safety Population	Yes	Yes
	14.3.4.1.1.3	Summary of Potentially Clinically Significant Hematology Results	Safety Population		Yes
	14.3.4.1.1.4	Listing of Subjects with Abnormal Hematology Results	Safety Population	Yes	
	14.3.4.1.1.5	Listing of Subjects with Potentially Clinically Significant Hematology Results	Safety Population	Yes	
14.3.4.1.2		Blood Chemistry Data			
	14.3.4.1.2.1	Summary of Laboratory Data - Chemistry	Population	Yes	
	14.3.4.1.2.2	Shift from Baseline for Chemistry by Reference Range	Safety Population	Yes	Yes
	14.3.4.1.2.3	Summary of Potentially Clinically Significant Chemistry Results	Safety Population		Yes
	14.3.4.1.2.4	Listing of Subjects with Abnormal Chemistry Results	Safety Population	Yes	
	14.3.4.1.2.5	Listing of Subjects with Potentially Clinically Significant Chemistry Results	Safety Population	Yes	
14.3.4.1.3		Urinalysis Data	·		
	14.3.4.1.3.1	Summary of Laboratory Data - Urinalysis	Safety Population	Yes	
	14.3.4.1.3.2	Summary of Potentially Clinically Significant Urinalysis Results	Safety Population		Yes
	14.3.4.1.3.3	Listing of Subjects with Potentially Clinically Significant Urinalysis Results	Safety Population	Yes	
14.3.4.2		Vital Signs			
	14.3.4.2.1	Summary of Vital Signs, Height and Weight	Safety Population	Yes	Yes
	14.3.4.2.2	Shift from Baseline in Vital Signs by Clinically Significant Abnormality	Safety Population	Yes	
	14.3.4.2.3	Summary of Potentially Clinically Significant Vital Signs and Weight	Safety Population		Yes
	14.3.4.2.4	Listing of Subjects with Clinically Significant Vital Signs	Safety Population	Yes	
14.3.4.3		Electrocardiogram (ECG) Data	•	1	
	14.3.4.3.1	Summary of Eletrocardiogram (ECG) Interpretation	Safety Population		
	14.3.4.3.2	Shift from Screening in Eletrocardiogram (ECG) Interpretation	Safety Population		
14.3.4.4		Other Safety	•		
	14.3.4.4.1	Summary of Physical Examination	Safety Population	Yes	
	14.3.4.4.2	Shift from Baseline in Physical Examination	Safety Population		

Sponsor: Galderma Research & Development, LLC; Protocol No.: RD.06.SPR.116912, Version 6.0

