Triglycerides	0.00	2.25	>4 at post-baseline, if baseline value ≤4	mmol/L	
LDH	NA	as in database	>3 x ULN at post-baseline, if baseline value ≤3 x ULN	mmol/L	
		uatabase	OLIV		
URINE					
Urine specific gravity	1.003	1.030	<0.995 at post-baseline, if baseline value ≥0.995		
			>1.038 at post-baseline, if baseline value ≤1.038		
Urine pH	5.00	8.00	<4.5 at post-baseline, if baseline value ≥4.5		
			>8.5 at post-baseline, if baseline value ≤8.5

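### The low urine specific-gravity flag in SAP Section 21 can never fire, 8 of 10 urinalysis parameters have no flag or shift table, and the one urinalysis table marked for the IDMC cannot show new protein, blood or glucose in urine

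*SAP*

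**What the plan says.** **What is measured.** Protocol Section 8.6.2.3 lists ten urinalysis parameters: specific gravity plus "pH, glucose, ketones, blood, protein, leukocytes, nitrites, bilirubin, urobilinogen". SAP Section 10.3 repeats the list. Protocol Section 6.2.3 places change from baseline in clinical laboratory values among the primary safety endpoints.

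**What is flagged.** The urine block of SAP Section 21 has two rows. The first gives the reference range, "Urine specific gravity 1.003 1.030", with a low flag of "<0.995 at post-baseline, if baseline value ≥0.995" and a high flag of ">1.038 at post-baseline, if baseline value ≤1.038". The second is pH, with reference range 5.00 to 8.00 and flags below 4.5 and above 8.5.

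**What is tabulated.** Protocol Section 9.4.3.4 plans absolute values, change from baseline and counts against the reference range for laboratory data, and adds: "Shift tables will be generated using the reference ranges". It makes no exception for urinalysis. SAP Section 10.3 is narrower: "Shift tables will be provided for hematology and chemistry by visit (scheduled visits only"). The listing of abnormal results ("out of reference range) will be provided for hematology and clinical chemistry") covers the same two panels. Urinalysis gets categorical counts by visit and a summary against the Section 21 ranges. SAP Section 14 foresees no change from the protocol's methods.

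**What the IDMC is sent by default.** In the SAP Section 18 index, the only urinalysis output marked for the IDMC is Table 14.3.4.1.3.2, "Summary of Potentially Clinically Significant Urinalysis Results".

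**The concern.** A flag table is useful to a monitoring committee only if its criteria can be met and cover the findings that matter. Here one of the four urine limits lies outside the range of the scale, and the parameters for which urinalysis is usually read (protein, blood, glucose) have no criterion at all. The one urinalysis table that goes to the IDMC by default would be silent on those parameters, and a reader could take that silence as reassurance.

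The final report has a related weakness. Every Section 21 flag is conditional on the subject's own baseline, so for specific gravity and pH the flag table separates new from pre-existing findings. For the other eight parameters no summary table does so: counts by visit give the number positive at each visit, not the number who became positive on treatment.

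**Working it through.** The plan states no derived figure to reproduce. The check is a count, a comparison of limits and a reading of the index.

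**1. Can the low specific-gravity flag fire?** Inputs from SAP Section 21: flag limit 0.995, reference range 1.003 to 1.030. One input is not in the documents: water has specific gravity 1.000, by definition of the scale.

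- Distance below water: 1.000 − 0.995 = 0.005.
- Distance below the SAP's lower reference limit: 1.003 − 0.995 = 0.008.

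No valid urine sample reads below 0.995, so the flag cannot fire, and its baseline condition (0.995 or more) is always met. This holds for any assumed water value of 0.995 or higher.

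**2. Are the other urine limits reachable?** All four limits are the reference limits moved outward by equal steps:

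- Specific gravity: 1.003 − 0.008 = 0.995 and 1.030 + 0.008 = 1.038.
- pH: 5.0 − 0.5 = 4.5 and 8.0 + 0.5 = 8.5.

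This pattern suggests mechanical widening that ran off the scale in one cell. Nothing in the documents makes the other three limits unreachable, so one limit of four is inoperable.

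**3. How many parameters have a criterion?** Ten are measured and two have a row: 10 − 2 = 8 without one. These are protein, blood, glucose, ketones, bilirubin, urobilinogen, nitrites and leukocytes.

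**4. Which outputs are marked for the IDMC (SAP Section 18)?**

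| Panel | By-visit summary | Shift from baseline | Flag table |
|---|---|---|---|
| Hematology | marked | marked | marked |
| Chemistry | not marked | marked | marked |
| Urinalysis | not marked (14.3.4.1.3.1) | no such table | marked (14.3.4.1.3.2) |

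The other two urinalysis outputs, Listing 14.3.4.1.3.3 (flagged subjects) and Listing 16.2.8.1.3 (all results), are marked for the interim analysis but not for the IDMC. So 1 of 4 urinalysis outputs is marked, and it uses 2 of 10 parameters.

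**5. What do counts by visit leave open?** With n subjects, b positive at baseline and w positive at Week 16, the number newly positive at Week 16 lies between max(0, w − b) and min(w, n − b). The documents give no values for b or w. Taking n = 20 and assuming b = w, for illustration only:

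- b = w = 2: from max(0, 0) = 0 to min(2, 18) = 2.
- b = w = 4: from 0 to min(4, 16) = 4.
- b = w = 6: from 0 to min(6, 14) = 6.

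The table alone cannot tell no new cases from all cases being new. The subject listing can.

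**The case against.** The strongest reply is that other routes carry the missing information.

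- Table 14.3.4.1.3.1 summarizes all urinalysis parameters by visit, and Listing 16.2.8.1.3 shows each subject's results. With about 20 subjects, onset can be read from the listing by eye.
- Under Protocol Section 8.6.2 the investigator evaluates every out-of-range result, and a clinically significant one that is new or worse since screening is to be reported as an adverse event. The main TEAE tables are marked for the IDMC.
- SAP Section 13 lets IDMC members ask for other outputs. The IDMC charter, which governs what they receive, is not available here.
- The protocol ties shift tables to reference ranges, which suits numeric results. SAP Section 21 gives urine reference ranges only for specific gravity and pH, so the promise is less clear for the dipstick parameters. Protocol Section 9.4.3.7 also leaves further safety detail to the SAP.
- No urinary or renal event is among the AESIs, and serum creatinine, glucose and bilirubin have flags of their own.

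Most of this stands, and it limits the point. A reader might infer that the urinalysis flags do not work at all, or that new urinary findings would go unseen. The documents support neither: three of the four limits can fire, and the routes above are real.

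Three things remain. The adverse event route depends on each investigator's judgment and is not a systematic display. A request from the IDMC presupposes that it notices that its table omits eight parameters. And the shift-table mismatch is clear at least for specific gravity and pH, while the change-from-baseline plan covers laboratory data without exception; SAP Section 14 mentions neither omission.

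The impossible limit and the coverage gap are separate faults. Correcting 0.995 would reveal no protein, blood or glucose.

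**Conclusion.** The point holds, and it is minor. One of four urine flag limits cannot fire; 8 of 10 urinalysis parameters have no criterion; the SAP drops urinalysis change from baseline and shift tables without recording the departure; and the only urinalysis table marked for the IDMC cannot, as written, show new protein, blood or glucose in urine. The gap is confined to the default IDMC pack and to the summary of onset. The data are collected, listed and counted by visit, so it would be wrong to conclude that urinary safety is unreported.

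This rests on three assumptions: water has specific gravity 1.000; the urine block of Section 21 is complete as read (it closes the document and looks whole, but a row elsewhere in that table has lost its limits, so extraction loss cannot be fully excluded); and the IDMC charter does not already ask for more urinalysis output than the SAP index shows.

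**What to change.** 1. In SAP Section 21, correct or delete the 0.995 entry after checking with the central laboratory.
2. Add to SAP Section 10.3 and the Section 18 index a categorical shift-from-baseline table for the urinalysis parameters. It needs no new thresholds, since it uses the result categories as reported. If the table is not wanted, record the departure from Protocol Section 9.4.3.4 in SAP Section 14.
3. Mark that table or Table 14.3.4.1.3.1 for the IDMC.

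Grade-based flags for the eight parameters are optional; they would have to be defined with the medical monitor.

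The cost is SAP wording and one extra table on data already collected, with no change to study conduct. The downside is that some benign findings will be on display, for example blood from menstruation.
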